4.1.7. Starting Dose

As noted in Studies 5326-04 and 5326-07, apilimod was found to be safe and well-tolerated at daily doses up to 100 mg/day as a single daily dose of apilimod dimesylate or BID at a total dose of 70 mg of apilimod (equivalent to apilimod dimesylate 100 mg). The starting dose selected for this Phase 1 dose escalation trial is LAM-002A 50 mg BID. This dose is expected to achieve a C_{max} of ~ 70-80 ng/mL, or 180 nM, with predicted plasma half-life of 5 - 10 hours. Concentrations required for 90% inhibition of highly sensitive NHL subtypes in *in vitro* assays is ~50 nM. It is acknowledged that this starting dose level will likely result in plasma levels over a 24-hour period that are lower than the *in vitro* concentrations cited; however, the LAM-002A 50-mg-BID dose for the first cohort is chosen to minimize the risk of potential toxicities in this highly pre-treated NHL population.

Dose escalation will proceed by a modified Fibonacci schema as outlined in Table 3. If additional dose exploration beyond the highest dose shown in Table 3 is required to define the maximum tolerated dose (MTD), then dose escalation may proceed at increments < 33%.

The subject population in this study will be comprised of subjects with B-cell NHL who have relapsed or were refractory to previous therapy (including at least one prior chemoimmunotherapy regimen), and failed or were ineligible or unwilling to undergo ASCT in the setting of DLBCL.

Version 9, 18 Feb 2020

5. TRIAL OBJECTIVES AND PURPOSE

The overall purpose of this Phase 1 study is to explore the safety and tolerability of LAM-002A when given alone and in combination for the treatment of subjects with relapsed or refractory B-cell NHL.

5.1. Primary Objectives

• To determine the maximum tolerated dose (MTD) of daily oral administration of LAM-002A in subjects with relapsed or refractory B-cell NHL

5.2. Secondary Objectives

- To evaluate the plasma pharmacokinetics (PK) of apilimod, and its active metabolites, administered orally in subjects with relapsed or refractory B-cell NHL
- To evaluate the safety and tolerability of daily oral administration of LAM-002A in subjects with relapsed or refractory B-cell NHL
- To evaluate the preliminary anti-tumor activity of LAM-002A

5.3. Exploratory Objectives

- To evaluate the pharmacodynamic effects of LAM-002A, administered orally, in plasma assays and surrogate tissue (gene expression in peripheral blood mononuclear cells [PBMCs]/B cells, and plasma cytokines [including (IL)-12 and IL-23]).
- To evaluate tumor and/or plasma for gene expression and genetic alterations (with saliva and/or B-cell-depleted PBMC collection for germ-line control) and surrogate tissue (PBMC/B cells) for gene expression that may predict anti-lymphoma activity.
- To evaluate plasma for changes in analytes or tumor for protein expression that may predict anti-lymphoma activity

5.4. Primary Endpoints

• Frequency of dose-limiting toxicities (DLTs) as a function of the dose of LAM-002A during the first cycle of treatment

5.5. Secondary Endpoints

- Standard PK parameters including but not limited to AUC, t_{1/2} and C_{max}
- The type and frequency of AEs, serious adverse events (SAEs) using National Cancer Institute (NCI) CTCAE v4.0 (Common Toxicity Criteria for Adverse Events, version 4.0) as well as changes in clinical laboratory values, electrocardiogram (ECG) parameters and vital sign measurements
- Response as assessed by the investigator according to modified Lugano Response Criteria for NHL (Cheson 2014) and revised guidelines for the diagnosis and treatment of CLL (Hallek 2008, Cheson 2012)

Version 9, 18 Feb 2020

5.6. Exploratory Endpoints

- Extent of PIK fyve inhibition as determined by plasma inhibitory assays
- Changes in gene expression in PBMCs
- Changes in plasma cytokines (including IL-12 and IL-23)
- Correlation between genetic alterations as determined by next generation sequencing and/or gene expression in tumor tissue, plasma (circulating tumor DNA), or PBMCs/B cells and anti-lymphoma activity following treatment with LAM-002A
- Correlation between changes in plasma bioanalytes or tumor protein expression and anti-lymphoma activity following treatment with LAM-002A as determined by proteomic tools

6. INVESTIGATIONAL PLAN

6.1. Overall Study Design

This is a Phase 1, single-arm, open-label, dose-escalation study of safety and PK of apilimod administered to subjects with refractory or relapsed B-cell NHL. This study will be conducted in 3 stages.

6.1.1. LAM-002A Dose Escalation Stage (Stage 1)

The maximum tolerated dose (MTD) will be determined during the dose-escalation stage, evaluating both continuous and intermittent dosing regimens. Subjects will accrue using a 3+3 design. During this stage, the decision to open a new cohort at a higher or lower dose level will be made by the participating clinical investigators and sponsor when all subjects in the current cohort have been treated through at least Week 4 or once 2 DLTs have occurred in that dose cohort. All available safety and PK data will be considered in a decision by the medical monitor in collaboration with the investigators to dose escalate, de-escalate, expand the current cohort or explore alternate regimens of drug administration. The MTD will be determined based primarily on DLTs observed through Week 4 in ≥ 6 subjects.

6.1.2. Expansion Stage (Stage 2)

Once the MTD and/or recommended phase 2 dose (RP2D) and schedule is determined, the study will enter the expansion stage, in which cohorts of subjects will be accrued in order to obtain additional information on safety, tolerability, preliminary anti-tumor activity, PK, and pharmacodynamic data at the RP2D and schedule when LAM-002A is administered alone or in combination with rituximab/rituximab hyaluronidase or atezolizumab. Expansion-stage cohorts will comprise groups of subjects with specific types of previously treated, relapsed, progressive, and measurable NHL who will receive LAM-002A monotherapy or LAM-002A-containing combination therapy as shown in Table 2. For both monotherapy and combination cohorts, the starting dose of LAM-002A will be 125 mg BID administered continuously.

Version 9, 18 Feb 2020

Table 2: Expansion Stage Disease Types and Therapies

Cohort Number	NHL Type	Investigational Drug	Combination Drug	Evaluable Subjects, n
1	FL	LAM-002A		Up to ~20
2	MZL	LAM-002A		6
3	DLBCL-GCB	LAM-002A		6
4	DLBCL-ABC	LAM-002A		6
5	FL or MZL	LAM-002A	Rituximab or rituximab hyaluronidase human	Up to ∼20 with FL
6	DLBCL-GCB or DLBCL-ABC	LAM-002A	Rituximab or rituximab hyaluronidase human	6
7	FL or MZL	LAM-002A	Atezolizumab	6
8	DLBCL-GCB or DLBCL-ABC	LAM-002A	Atezolizumab	6

Abbreviations: ABC: activated B-cell (subtype); DLBCL: diffuse large B-cell lymphoma; FL: follicular lymphoma; GCB: germinal center B-cell (subtype); MZL: marginal zone lymphoma; NHL: non-Hodgkin lymphoma

6.1.3. Extension Stage (Stage 3)

The extension stage (Stage 3) can begin once the last study subject has completed at least 8 cycles of study treatment. At this time, the study sponsor will conclude the dose-escalation and expansion stages of the study, will collate and verify all study data through an appropriate data cutoff date, and will lock the study database for preparation of a study report. Subjects who are still safely benefiting from Stage 1 or Stage 2 study therapy as of the data cutoff date may electively continue their current regimen of study therapy in Stage 3, receiving clinical care and diagnostic testing consistent with conventional practice standards as deemed appropriate by the treating investigator. Therapy in Stage 3 may continue in the absence of protocol-defined reasons to discontinue therapy. During Stage 3, collection of clinical data by the sponsor will be limited to serious adverse event (SAE) reports. Study drug accountability will be managed per site procedures; relevant pharmacy records may be collected by the sponsor to document study drug disposition.

6.1.4. Subject Allocation (Stage 1 and Stage 2)

Subjects will be allocated to the cohorts by the study sponsor working in collaboration with each investigator considering the availability of openings for enrollment in Stage 1 or 2, disease type (i.e., FL, MZL, DLBCL-GCB, DLBCL-ABC, or other indications), therapy history (e.g., prior use of anti-CD20 or anti-PD1/PDL1 antibodies), and current disease status (e.g., potential to benefit from rituximab treatment based on past responses to anti-CD20 antibody therapy).

During Stage 1 dose ranging with LAM-002A monotherapy, allocation will be performed according to a 3+3 dose-escalation procedure with the requirement that each cohort of 3 subjects be observed for ≥4 weeks before another cohort is enrolled (as detailed in Section 6.6). During Stage 2 cohort expansion evaluating LAM-002A monotherapy, allocation will be performed as subjects present to the accruing clinics and there will be no specific restrictions on the cadence of enrollment. During Stage 2 cohort-expansion of LAM-002A combinations with rituximab and

Version 9, 18 Feb 2020

atezolizumab, enrollment of the first 3 subjects in each combination cohort will be restricted such that each subject must be enrolled sequentially and observed for \geq 3 weeks before the next subject is enrolled. Beginning with the 4th patient in each combination group, further enrollment may proceed without restriction as long as the continuous reassessment boundaries for toxic drug discontinuations are not met (as detailed in Section 6.8.4.4 and Section 14.1.2).

6.1.5. Subject Evaluability

A Stage 1 subject will be considered evaluable if the subject meets the definition for evaluability of Cycle 1 DLT as described in Section 6.6. A Stage 2 subject will be considered evaluable if the subject has both baseline and ≥ 1 on-study tumor assessments sufficient to allow a determination of response to study therapy.

6.2. Number of Subjects

As many as 145 subjects will be enrolled, assuming that:

- In the dose-escalation stage of the study, the total number of subjects will depend upon the numbers of subjects accrued to each dose level and the number of dose levels evaluated. If 6 subjects are enrolled at all open starting dose levels (Dose Levels 5, 6, 7, and 8) and 6 additional subjects are enrolled at the MTD or RD, as many as 30 subjects could be enrolled. To allow for the possibility that some subjects may not be fully evaluable for DLT or that an intermediate dose level might be evaluated, up to ~45 subjects may be enrolled.
- In the expansion stage of the study, if all 8 potential expansion cohorts are accrued, as many as ~76 subjects could be enrolled. To allow for the possibility that some subjects may not be fully evaluable for efficacy or to establish bounds on efficacy estimates with greater confidence, up to ~100 subjects may be enrolled.
- In the extension stage of the study, the total number of subjects will include ≤4 subjects who have participated in the expansion stage of the study and are still receiving study therapy on the data cutoff date that concludes the dose-escalation and expansion stages of the clinical trial.

6.3. Randomization and Blinding

This is an open-label study and there is no randomization of subjects.

6.4. Treatment Assignment

Inclusion and exclusion criteria will be reviewed for each potential subject by the investigator. If the consented subject is eligible for study participation, the site will send the eligibility form to Ce3 (see Study Manual).

Ce3 will review the subject's eligibility form to confirm each subject's eligibility and will complete the enrollment form with treatment cohort, treatment dose and frequency. The enrollment form will be signed and a copy sent to the study site. Once the site receives the completed enrollment form, the subject will begin treatment accordingly. The treatment will be conducted in an open-label manner. Study sites cannot start dosing the subject without receiving the assigned dose on the returned Subject Enrollment and Eligibility Form.

Version 9, 18 Feb 2020

Subject identification (ID) will be in the format of Site XXX-Subject XXX, for example, 001-001 is for Site 001 first subject. Site ID will be assigned consecutively and subject ID will be sequential per site.

Subject replacement is described in Section 6.13

6.5. Overall Treatment Periods

6.5.1. Pre-Treatment Period

The subject is consented and undergoes screening assessments to be qualified for the study. The Schedule of Assessments can be found in Section 8.7.

6.5.2. Treatment Period

The subject is treated and monitored for safety (including assessments of AEs, vital signs, ECGs, laboratory tests and concomitant medications). Additionally, preliminary anti-tumor activity will be assessed and PK and biomarker samples will be collected.

6.5.3. Post-Treatment Period

Subjects should be followed until the later of either 30 days after the last dose of study treatment or until resolution/stabilization of any ongoing drug-related AEs and/or SAEs. For subjects with events that require follow-up, information regarding concomitant medications should be collected. Any necessary follow-up may be obtained in person or by telephone contact.

Subjects who have discontinued study treatment for reasons other than PD will be assessed per Revised Response Criteria for NHL or Guidelines for the diagnosis and treatment of CLL at a minimum of every 12 weeks until documentation of PD, start of new anti-cancer therapy or for up to 1 year from the last enrolled subject's first treatment (Cycle 1 Day 1) whichever comes first.

Long-term follow-up survival information will be obtained in all surviving subjects who permanently discontinue study therapy. Such information may be collected at ~3- to 6-month intervals at the sponsor's discretion through 3 years. This long-term follow-up information will be gathered during routine clinic visits, other study site contact with the subjects, or via telephone or e-mail with the subjects/caregivers or referring physician offices.

6.6. LAM-002A Dose-Escalation Procedures

LAM-002A will be administered on a twice daily (BID), or thrice daily (TID) oral dosing regimen with a cycle length of 28 days. Subjects on a BID schedule will be advised to take the doses at the same time each day, ~12 hours apart. Subjects on a TID schedule will be advised to take the doses at the same time each day at intervals of ~6 to 8 hours. On PK days, subjects on a TID schedule should receive the morning dose and complete the blood collections through 8 hours thereafter before taking the second dose on that day.

Other drug administration schedules may be considered if the initial BID or TID regimen's safety, PK and/or pharmacodynamics suggest that a different schedule would be better tolerated and might allow for serum exposures required for anti-lymphoma activity. This might include a treatment break such as 3 weeks on/1 week off treatment or 5 days on/2 days off over a 4-week

Version 9, 18 Feb 2020

cycle or an asymmetric (AM dosing > PM dosing) or once-daily dosing schedule. If another treatment regimen is evaluated, then the initial dose tested on this schedule will be no higher than the total daily dose that has been previously evaluated and tolerated.

Cohorts of 3 to 6 subjects will be sequentially enrolled at progressively higher starting dose levels of LAM-002A, as indicated in Table 3. The initial cohort of subjects will be prescribed LAM-002A at Dose Level 0 (50 mg BID). Dose level -1 (25 mg BID) is provided to permit a dose decrement in subjects experiencing DLT at Dose Level 0.

Table 3: LAM-002A Provisional Starting Dose Levels

Continuous Administration				
Dose Level	LAM-002A Dose and Schedule	LAM-002A Total Daily Dose		
-1	25 mg BID	50 mg		
0 (Initial Dose Level)	50 mg BID	100 mg		
1	100 mg BID	200 mg		
1a	125 mg BID	250 mg		
1b	75 mg TID	225 mg		
1c	100 mg TID	300 mg		
1d	125 mg TID	375 mg		
2	150 mg BID	300 mg		
3	200 mg BID	400 mg		
4	275 mg BID	550 mg		
Intermittent Administration	Intermittent Administration			
Dose Level	LAM-002A Dose and Schedule	LAM-002A Total Daily Dose		
5	150 mg BID	300 mg		
6	200 mg BID	400 mg		
7	250 mg BID	500 mg		
8	300 mg BID	600 mg		

Abbreviations: BID: Twice daily (or 2 times per day); TID: Thrice daily (or 3 times per day)

A 3 + 3 design will be utilized to define an MTD. For cohorts consisting of 3 subjects, dose escalation to the next higher dose may proceed if no DLT is observed within the first cycle of the 3 evaluable subjects accrued to a cohort (See Section 6.1.1). If 1 of 3 subjects in the cohort experiences a DLT, up to a total of 6 evaluable subjects will be enrolled. If 2 or more of the 3-6 evaluable subjects in a cohort experience a DLT, dose escalation will cease, and additional subjects will be treated at a lower dose level or with another schedule. If de-escalation to the previous dose cohort is undertaken, this cohort may be expanded to \geq 6 subjects. Additional subjects (up to 12 total per cohort) may be evaluated to refine the estimation of the MTD and RP2D at the planned dose levels or at an intermediate dose level between the highest previously tolerated total dose and the next planned total daily dose. The MTD is defined as the highest dose at which \leq 33% of subjects experience a DLT in the total dose cohort.

Dose escalation decisions will be evaluated in a DLT-evaluable population. The DLT-evaluable population will include subjects who complete Cycle 1 dosing or who are withdrawn from study due to a DLT in Cycle 1. A subject will be deemed non-evaluable for determining DLTs and will not be counted toward the total cohort size if the subject did not experience a DLT, did not

receive at least 75% (42/56 BID schedule; 63/84 TID schedule, 18/24 intermittent schedule) of the planned first-cycle doses or discontinued from the study prior to completing necessary safety evaluations through the first 28 days of study treatment. These subjects may be replaced unless accrual to the cohort has stopped due to DLT.

Following the above guidelines, the participating investigators and sponsor will review available data including toxicity, PK and anti-tumor activity data to reach consensus on dose levels and determination of the MTD. This group will review available safety data for each cohort and will determine whether the MTD has been reached and decide upon further subject enrollment. Any detected cumulative toxicity may require later dose reductions or other action as appropriate, and may be evaluated in determining the RP2D and schedule.

The RP2D and schedule will be determined in discussion between the sponsor and participating investigators. Observations related to PK, pharmacodynamics and any drug-related toxicities may be included in the rationale supporting the RP2D and schedule.

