6.7. Definition of LAM-002A Dose-Limiting Toxicity (DLT)

A DLT will be defined as an AE or abnormal laboratory value meeting the criteria in Table 4 and that is assessed as unrelated to disease, a comorbid condition, intercurrent illness, or concomitant medications). For the purposes of dose escalation and determination of the LAM-002A MTDs, DLTs that occur within the first cycle of treatment must be included in decisions regarding dose escalation. DLTs or other clinically significant toxicities that occur after Cycle 1 may also be considered when determining the RP2D.

Table 4: Criteria for Defining Dose-Limiting Toxicities (DLTs)

Toxicity	Criteria
Hematology	CTCAE Grade 4 neutropenia lasting ≥ 7 days
	CTCAE Grade 4 febrile neutropenia
	CTCAE Grade 3 thrombocytopenia with bleeding that requires transfusion therapy
	CTCAE Grade 4 thrombocytopenia
Toxicity	Criteria
Gastrointestinal	≥ CTCAE Grade 3 vomiting or nausea despite the use of optimal anti-emetic treatments
	≥ CTCAE Grade 3 diarrhea despite the use of optimal anti-diarrheal treatments
Renal	Serum creatinine > 3.0 x ULN
Hepatic	Total bilirubin ≥ CTCAE Grade 3
	Total bilirubin ≥ CTCAE Grade 2 and ALT or AST ≥ CTCAE Grade 2
	or,
	for subjects with liver metastases at baseline, total bilirubin \geq 2.0 x ULN and ALT or AST \geq CTCAE Grade 3

Version 9, 18 Feb 2020

Toxicity	Criteria	
Treatment interruption/delays	Inability to administer ≥28/56 (BID schedule) or ≥42/84 (TID schedule) or ≥12/24 (intermittent schedule) planned LAM-002A doses in a treatment cycle due to drug-related AEs	
	or	
	Failure to recover from LAM-002A-related toxicities to baseline within 14 days from the last dose of LAM-002A in a cycle	
Other adverse events not listed above	Non-hematologic toxicities of CTCAE ≥ Grade 3 except for the following. • Alopecia • CTCAE Grade 3 forigue for < 72 hours	
	• CTCAE Grade 3 fatigue for < 72 hours	
	 Asymptomatic Grade 3 elevations in biochemistry laboratory values that last for ≤ 7 days that are not deemed to be clinically relevant. This includes electrolyte abnormalities that respond to medical intervention. 	
	Any LAM-002A-related adverse event that, in the opinion of the investigator, requires a dose reduction or discontinuation of treatment.	

Abbreviations: ALT: Alanine aminotransferase; AST: Aspartate aminotransferase; CTCAE: Common terminology criteria for adverse events; DLT: Dose-limiting toxicity; ECG: Electrocardiogram; NHL: Non-Hodgkin lymphoma; ULN: Upper limit of normal

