8.6. Treatment Compliance

The investigator will dispense the study medication only for use by subjects enrolled in the study as described in this protocol. The study medication is not to be used for reasons other than those described in this protocol.

The investigator or other study staff will supervise LAM-002A treatment given at the site and instruct the subject on study medication self-administration. Subjects will be asked to bring their dosing diary with them at each visit. Compliance with protocol-defined LAM-002A intake will be checked by pill count at the end of each cycle and compliance decisions will be made by the investigator.

A subject is considered to be DLT-evaluable if he/she has taken at least 75% (42/56 BID schedule; 63/84 TID schedule, 18/24 intermittent schedule) of the planned first-cycle doses and has sufficient safety data, or has experienced a DLT in the first cycle.

Version 9, 18 Feb 2020

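### Some Cycle 1 subjects who miss between a quarter and half of their doses because of LAM-002A toxicity are neither DLTs nor evaluable, and may be replaced

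*Combined protocol and SAP*

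**What the plan says.** Escalation decisions use a DLT-evaluable population (Section 6.6). For a subject without a DLT, 6.6 states: "A subject will be deemed non-evaluable for determining DLTs and will not be counted toward the total cohort size" if he or she did not "receive at least 75% (42/56 BID schedule; 63/84 TID schedule, 18/24 intermittent schedule) of the planned first-cycle doses". The cause of the shortfall plays no part. Section 8.6 repeats the 75% floor from the other side: a subject is evaluable who reached it and "has sufficient safety data, or has experienced a DLT in the first cycle". On replacement, 6.6 adds: "These subjects may be replaced unless accrual to the cohort has stopped due to DLT". Section 6.13 leaves replacement to the sponsor's discretion.

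Table 4 in Section 6.7 treats dose interruption as a DLT at a different level: inability to give ≥28/56, ≥42/84 or ≥12/24 "planned LAM-002A doses in a treatment cycle due to drug-related AEs". A second interruption criterion is "Failure to recover from LAM-002A-related toxicities to baseline within 14 days from the last dose of LAM-002A in a cycle". A further line, at any grade, covers a LAM-002A-related event that the investigator judges to need dose reduction or discontinuation.

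Under Section 6.1.1 the decision to open a new cohort can be taken "when all subjects in the current cohort have been treated through at least Week 4", or earlier once two DLTs have occurred. The MTD rests primarily on DLTs through Week 4, with all available safety and PK data considered.

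**The concern.** The evaluability floor is 75% and the missed-dose DLT criterion sits at about 50%. Between them lies a band in which a subject can lose a substantial part of Cycle 1 dosing to the drug and count neither as an event nor in the denominator.

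This missingness is informative. The introduction (4.1.4.3) describes dose-dependent nausea, vomiting and diarrhea, and 6.8.2.5 says these typically begin soon after dosing starts. Gastrointestinal events reach DLT level on severity only at Grade 3 or above despite optimal supportive care. Repeated missed doses for Grade 2 symptoms that then resolve need not meet any criterion. The primary endpoint is the Cycle 1 DLT frequency by dose (5.4), so replacing such subjects would tilt the evaluable group toward those who tolerate the dose.

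**Working it through.** **The band, by dose count.** The minimum for evaluability (6.6, 8.6) is set against the missed-dose criterion (Table 4).

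| Schedule | Planned | Evaluable if received | Missed doses in the band | Exactly half |
|---|---|---|---|---|
| BID | 56 | ≥42 | 15–27 | 28 |
| TID | 84 | ≥63 | 22–41 | 42 |
| Intermittent | 24 | ≥18 | 7–11 | 12 |

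Exactly half is ambiguous. If ≥28/56 counts missed doses, 28 missed is a DLT. If it means that 28 could not be reached, a subject given exactly 28 is still in the band. The intermittent schedule is four courses of six doses per cycle (6.8.2.3, 6.8.2.6.2), so losing two whole courses gives exactly 12 of 24.

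**The plan's own figure.** Under the 3+3 rule, with DLT probability p,

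P(escalate) = (1−p)³ + 3p(1−p)² × (1−p)³.

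At p = 0.10, 0.20, 0.30, 0.40, 0.50 and 0.60 this gives 0.906, 0.709, 0.494, 0.309, 0.172 and 0.082. Rounded, these are all six entries of Table 14. The formula takes every subject as evaluable and does not model replacement.

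**Adding the band.** Let d be the DLT rate from the other criteria, g the share of subjects in the band because of toxicity, and f the fraction of g already made DLTs by the dose-reduction or discontinuation criterion. Assume that every uncaught band subject is replaced. The value of p in the formula is then:

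- as written: (d + gf) / (1 − g(1−f))
- if band subjects all count as DLTs: d + g
- if uncaught band subjects stay in as evaluable non-DLTs: d + gf

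The documents give none of d, g or f. With d = 0.10 and g = 0.20 as assumptions:

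| f | p as written | P(escalate) as written | All band subjects DLTs (p = 0.30) | Uncaught kept as non-DLTs |
|---|---|---|---|---|
| 0 | 0.10/0.80 = 0.125 | 0.862 | 0.494 | 0.906 |
| 0.5 | 0.20/0.90 = 0.222 | 0.660 | 0.494 | 0.709 |
| 1 | 0.30/1.00 = 0.300 | 0.494 | 0.494 | 0.494 |

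With f = 0 and d and g each between 0.10 and 0.30, the difference between the as-written and all-DLT figures runs from 0.12 (0.428 − 0.309, at d = 0.30, g = 0.10) to 0.52 (0.828 − 0.309, at d = 0.10, g = 0.30). With f = 1 it is zero throughout.

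**Timing of the recovery criterion.** With continuous dosing the last Cycle 1 dose can fall on Day 28, and 28 + 14 = Day 42. With intermittent courses starting on Days 1, 8, 15 and 22, the last dose is on Day 24, and 24 + 14 = Day 38. Both fall after Week 4.

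**The case against.** The strongest reply is that Table 4 already catches many of these subjects. Its dose-reduction or discontinuation line has no grade or missed-dose threshold. Section 6.8.2.5 says that after an interruption for a DLT or another AE requiring dose modification, the dose should be reduced on resumption. On BID dosing, 15–27 missed doses is about 7.5 to 13.5 days off drug, and a hold that long may well end in a reduction. A reader might infer that everyone who misses 25–50% of doses for toxicity escapes both rules. The documents do not support that. What remains is the subject with lower-grade toxicity who misses doses, recovers, and resumes without a reduction. That path is open: under 6.8.2.4 a BID dose delayed by six hours or more is not taken, and under 6.8.2.3 a toxicity-related break in the intermittent cadence calls for consultation with the medical monitor, not a mandatory reduction.

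A reader might also infer that the MTD decision ignores this intolerance. It need not. Replacement is optional, all safety data are reviewed (6.1.1, 6.6), drug-related toxicities may inform the RP2D (6.6), and these subjects stay in the full analysis set (14.3.1). But no rule says what weight they carry, and the formal count leaves them out.

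Two further points stand. Section 6.2 lists only the intermittent Levels 5–8 as open, with mandatory antiemetic prophylaxis, so 7–11 of 24 is the band that matters for those cohorts. And Week 4 is a minimum, so the recovery criterion is a lesser inconsistency: the sponsor may wait, but the text does not require it.

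**Conclusion.** The point holds in a limited form. Sections 6.6 and 8.6, read with Table 4, leave a band of more than 25% and less than 50% of doses missed, with exactly half unclear. A subject in it because of LAM-002A toxicity, with no dose reduction, discontinuation or other Table 4 event, is non-evaluable and may be replaced. This removes drug-caused intolerance from the primary DLT count.

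The size cannot be fixed from the documents. The contrast of 0.86 with 0.49 should not be read as the plan's actual error. It needs 10% formal DLTs, 20% of subjects in the band, none caught elsewhere, all replaced, and the view that each should have been a DLT. If half are caught it is 0.66 against 0.49, and if all are there is no difference. Nor is the direction automatic: kept as evaluable non-DLTs, the same subjects would raise the probability of escalating from 0.862 to 0.906. The defect is that the plan does not say how they count.

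**What to change.** - In 6.6 and 8.6, limit non-evaluable and replaceable status to shortfalls not caused by LAM-002A-related AEs.
- Reconcile 6.6 and 8.6 with Table 4 so that no toxicity-caused shortfall falls between the two rules. State whether such a subject enters the 3+3 count as a DLT or as an evaluable non-DLT. The cut-off and that classification are for the sponsor and investigators.
- Say whether ≥28/56, ≥42/84 and ≥12/24 count doses missed or doses given.
- Report replaced subjects by dose level and reason.
- Secondary: reconcile the 14-day recovery criterion in Table 4 with the Week 4 decision point in 6.1.1, for subjects whose LAM-002A-related toxicity is unresolved at that time.

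The cost is a few sentences, possibly slower escalation, and a delay of up to about two weeks (Day 28 to Day 42) in some cohort decisions.
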